**Background, Rationale and Context**

Almost all Americans with end-stage kidney disease (ESKD) initiating hemodialysis (HD) are prescribed a dialysis regimen of fixed frequency (thrice-weekly) and fixed dose (dialysis single-pool Kt/V urea [spKt/Vurea]  $\geq 1.2$ , corresponding to standard Kt/Vurea [stdKt/Vurea]  $\geq 2.1$ ).

The target HD treatment dose was validated in trials that involved solely chronic HD patients (i.e., dialysis vintage >2years) with virtually no residual kidney function (RKF); this was then extrapolated as ‘optimal’ dialysis dose to all patients prescribed intermittent HD. In contrast, patients initiating peritoneal dialysis (PD) have the dialysis prescription adjusted according to RKF such that the initial PD regimen consists of shorter dialysis sessions with fewer exchanges; this approach was tested in clinical trials. Hitherto, the optimal HD regimen (frequency and dose) for patients with incident ESKD is not known as it has not been studied.

The most common cause of ESKD is progression of chronic kidney disease (CKD), a condition characterized by gradual loss of glomerular filtration over time. More than 90% of incident dialysis patients have an estimated glomerular filtration rate (eGFR)  $\geq 5\text{ml}/\text{min}/1.73\text{m}^2$  at dialysis initiation; this RKF helps regulate the volume status, maintain phosphate and potassium clearance, and, when pharmacologically enhanced with adjuvant medical therapy, could allow safe and effective introduction of an incremental HD regimen. Chin et al. analyzed the feasibility of incremental HD among incident ESKD patients in the United States by estimating the proportion of patients that could have started maintenance HD with a twice-weekly schedule based on four criteria: RKF; ultrafiltration rate; intradialytic blood pressure; and intradialytic symptoms. Based on their model, the authors concluded that more than half of the patients with

incident ESKD could be treated with incremental HD. Retrospective and observational studies showed that a regimen of twice-weekly HD at dialysis initiation may confer better RKF preservation than thrice-weekly HD treatment. Patients with higher levels of RKF generally reported better quality of life and had longer survival on HD than those with lower levels of RKF. In addition, residual glomerular filtration may allow removal of protein-bound uremic solutes that HD does not adequately remove. Thus, an incremental HD regimen could be employed in many patients with ESKD as a result of CKD progression and may have the potential to offer better patient outcomes.

Although beneficial effects of incremental HD on RKF and mortality were noted in previous reports, residual bias lingers even after rigorous adjustment for a variety of important covariates, owing to the nature of study design. A well-designed and executed prospective, randomized trial will offer superior data on the efficacy and safety of incremental HD in order to determine the optimum approach to the initiation of dialysis in patients with incident ESKD.

## **Objectives**

The primary objective of this study is to evaluate the feasibility and safety of incremental HD in incident ESKD patients. The secondary objectives are to evaluate the effects of HD frequency on changes in RKF, clinical and laboratory parameters (i.e., volume management, solute clearance, hospitalization rate), quality of life, and patient survival.

## **Hypothesis**

Patients with ESKD as a result of CKD progression have sufficient RKF such that an initial dialysis regimen of twice-weekly HD plus adjunctive pharmacologic therapy (loop diuretics, potassium-binding agent, and sodium bicarbonate) will afford adequate solute and volume control.

Compared to the conventional HD regimen, a gradual HD regimen with supportive pharmacologic therapy will confer better preservation of RKF.

## **Methods and Measures**

### **Design**

This randomized pilot trial will be parallel-arm in design. We will enroll 50 patients of age  $\geq 18$  years, with incident ESKD. Participants will be equally randomized to one of the two regimens: a) twice-weekly HD plus adjunctive pharmacologic therapy (loop diuretic, potassium-binding agent, and sodium bicarbonate) for six consecutive weeks, continued by thrice-weekly HD (intervention group); or b) thrice-weekly HD (comparator group) (Appendix A). Patients will be followed for 12 months after the date of randomization; or until transplant, death, withdrawal of consent, or transfer of care outside Wake Forest healthcare system, whichever occurs sooner. Feedback from the participants will be obtained during the study to (1) evaluate the delivery of study-related information, (2) evaluate coordination of care during the study as it pertained to study-related procedures, (3) evaluate patient perceptions on study-related assessments, (4) elicit patients' motivations for study participation, and (5) obtain participant input regarding future research concerning the study intervention.

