Dialysis prescription (HD treatment time and frequency of administration, achieved blood flow, dialysate flow, potassium and calcium dialysate baths), vascular access used for HD, target weight (TW), inter-dialytic weight gain (IDWG), and ultrafiltration rate (UFR) will be recorded throughout the study. Relative IDWG will be expressed as percentage of TW when divided by the nephrologists' determined target weight. All hospitalizations and deaths (along with the cause) will be recorded from the time of enrollment to study end.

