### ***Primary safety outcomes***

Time point: end of month 3

The intervention of stepwise HD schedule will be considered safe, relative to standard HD schedule, if there will be no significant difference in severe adverse events between the two HD treatment groups during the first 3 months of the study.

Severe adverse event(s) will be defined as the requirement of one or more additional HD treatment(s) or hospitalization(s) for: (1) a condition related to poor volume control (i.e., clinically-determined volume overload, decompensated heart failure, or hypertensive urgency/emergency); (2) severe electrolyte imbalance (i.e., serum potassium  $>6.5\text{mEq/L}$ ); (3) severe metabolic acidosis (i.e., serum bicarbonate  $<15\text{mEq/L}$ ); (4) symptomatic uremia (i.e., uremic encephalopathy, uremic pericarditis); or (5) death associated with study intervention.

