For evaluation of primary safety end points and secondary clinical end points, intention-to-treat principles will be followed. Evaluation of categorical end points will be performed using chi-squared tests. Evaluation of continuous end points will be performed using Student's unpaired t-test for normally distributed variables, or the Wilcoxon rank-sum test for nonparametric data. For comparison of variables measured during the time course of the study, a repeated measures analysis of variance (ANOVA) will be used. The consistency of effects on the primary end point will be explored in a variety of subgroups. Kaplan–Meier methods will be used for time-to-first hospitalization analyses. Missing RKF data for subjects will be replaced (rather than excluding them from the analysis, as missing RKF measurements might not be completely at random) using linear regression to estimate values based on other measurements for each subject (linear trend at point, SPSS). For each group-sequential analysis, the upper bound of the one-sided confidence interval for the hazard ratio (incremental HD to conventional HD) would be calculated with the use of the critical value from the Lan–DeMets–O'Brien–Fleming alpha-spending function, which preserves an overall one-sided alpha of 0.025. No adjustments for multiplicity will be made. An independent Safety Monitoring Committee will review all available data on a quarterly basis. Analyses that signal safety concerns (i.e., higher rates of hospitalization, treatment failure or death in the intervention arm compared to the comparator arm) will be reported to an independent Steering Committee to determine whether the study should be discontinued, be modified and then proceed, or continue with caution.

Descriptive statistics will be used to report the results of Participant Feedback Questionnaire.

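### Follow-up ends at transfer of care even inside the 3-month safety window, and the plan does not say how a transferred patient enters the intention-to-treat safety comparison

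*Combined protocol and SAP*

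**What the plan says.** All references are to the combined protocol and SAP.

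- **Design.** "Patients will be followed for 12 months after the date of randomization"; this is cut short by any of several events: "or until transplant, death, withdrawal of consent, or transfer of care outside Wake Forest healthcare system, whichever occurs sooner". No distinction is drawn between stopping study procedures and stopping safety follow-up.
- **Primary safety outcomes.** The stepwise schedule is judged safe if "there will be no significant difference in severe adverse events between the two HD treatment groups during the first 3 months". The event is a composite: "Severe adverse event(s) will be defined as the requirement of one or more additional HD treatment(s) or hospitalization(s) for" listed causes, with intervention-associated death also included.
- **Analytical Plan, population.** "For evaluation of primary safety end points and secondary clinical end points, intention-to-treat principles will be followed".
- **Analytical Plan, test.** The general rule on tests reads: "Evaluation of categorical end points will be performed using chi-squared tests". The safety outcome is not named in that sentence.
- **Analytical Plan, incomplete data.** A replacement rule is given for residual kidney function only. "Kaplan–Meier methods will be used for time-to-first hospitalization analyses"; no such method is assigned to the 3-month safety outcome. Drop-out is to be described by arm, as part of feasibility.
- **Data collection.** "All hospitalizations and deaths (along with the cause) will be recorded from the time of enrollment to study end". Additional dialysis sessions are not in that sentence. Dialysis frequency is to be recorded throughout the study, but no source outside the health system is named.

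**The concern.** An intention-to-treat comparison of proportions at month 3 needs a status for every randomised patient. Design allows observation to stop before month 3 for a reason that is neither death nor withdrawal of consent. The plan then has no status for that patient after the stop and no rule for supplying one.

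The direction of the possible error matters more here than in a superiority comparison. The favourable verdict is a non-significant difference, so each intervention-arm event that goes unseen makes that verdict easier to reach. Safety is part of the primary objective, and Human Subjects Protection rates the study as high risk. The comparison is also open: patients and staff know the schedule, so it cannot be assumed that leaving is unrelated to how a patient is doing. The documents say nothing about why patients transfer.

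**Working it through.** **Step 1. What is observed after a transfer before month 3.** Take each component of the safety event in turn.

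| Component | If study end means the patient's own end of follow-up | If study end means the end of the trial |
|---|---|---|
| Additional dialysis sessions at an outside unit | Not recorded | No stated source |
| Hospitalizations | Not recorded | Recorded under Data collection, in conflict with Design |
| Deaths | Not recorded | Recorded under Data collection, in conflict with Design |

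The gap for additional sessions stands on both readings. The gap for hospitalizations and deaths depends on a term that the plan does not define.

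**Step 2. Which patients matter.** The event is one or more occurrences, so a patient with a qualifying event before transfer is already counted. Only a first event after transfer and before month 3 can be lost.

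**Step 3. Size: what the plan provides.** Sample Size gives 2 × 25 = 50 patients, chosen by pilot-study convention. No event rate, transfer rate, power or safety margin is given, so there is no figure of the plan's own to reproduce. Everything below uses assumed counts and an assumed two-sided 0.05 level.

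**Step 4. Effect of one lost event.** The uncorrected Pearson statistic is χ² = N(ad − bc)² / (n₁ n₂ m₁ m₀), where a and b are intervention patients with and without an event, c and d the same for the comparator, n₁ and n₂ the arm sizes, and m₁ and m₀ the totals with and without an event.

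- 8/25 v 2/25: ad − bc = 8×23 − 17×2 = 150; χ² = 50×150² / (25×25×10×40) = 4.50; p = 0.034.
- One intervention event unseen and the patient scored event-free, 7/25 v 2/25: ad − bc = 7×23 − 18×2 = 125; χ² = 50×125² / (25×25×9×41) = 3.39; p = 0.066.
- The same patient dropped, 7/24 v 2/25: ad − bc = 7×23 − 17×2 = 127; χ² = 49×127² / (24×25×9×40) = 3.66; p = 0.056.

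Either handling crosses 0.05 in this example. The example sits at the boundary by choice. With Yates correction, 8 v 2 is already non-significant (χ² = 50×(150 − 25)² / 250,000 = 3.125; p = 0.077). Crossings then occur at other counts: 8 v 1 to 7 v 1 with Yates (0.027 to 0.054), and 7 v 1 to 6 v 1 with Fisher's test (0.049 to 0.098).

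**Step 5. How many events might be lost.** Assume 4% to 12% of an arm transfers by month 3: 0.04×25 = 1 to 0.12×25 = 3 patients. Assume an intervention risk of 8/25 = 32%, half the window unobserved, events spread evenly over it, and transfer unrelated to risk. The expected loss is 1×0.32×0.5 = 0.16 to 3×0.32×0.5 = 0.48 events, which is under one. It would be larger if patients who are deteriorating are the ones who leave.

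**Step 6. Effect on power.** Assume true risks of 30% v 5%, 25 per arm, and the uncorrected test enumerated exactly over binomial outcomes, with unseen events scored as event-free.

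| Share of events unobserved | Intervention arm only | Both arms |
|---|---|---|
| 0% | 0.71 | 0.71 |
| 8% | 0.64 | 0.66 |
| 12% | 0.60 | 0.64 |
| 20% | 0.52 | 0.59 |

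**The case against.** **Scoring.** A reader might infer that the plan scores a transferred patient as event-free. It does not say so. It is silent, and worst-case scoring, exclusion or censoring are equally open. The chi-squared test is also only the likely method: the Analytical Plan assigns it to categorical end points in general, and its monitoring text refers to a hazard ratio whose end point is unnamed. This stands. The defect is the absence of a rule together with a stop to observation.

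**Data collection.** A reader might also infer that all hospitalizations and deaths after transfer are lost. If study end is the end of the trial, they are to be recorded. This stands in part: it narrows the firm gap to outside dialysis sessions, but it contradicts Design and names no way to obtain outside data.

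**Provisions already made.** Kaplan–Meier censoring accommodates early exits for time to first hospitalization, leaving only the question of informative exit. The planned drop-out description partly meets the need to report losses by arm. Neither settles the 3-month safety comparison.

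**Size.** The planned schedules differ for six weeks only. After a transfer at the end of week 4, two of the eight unobserved weeks (5 to 12) fall in that period. The expected loss in Step 5 is below one event. Much of the fragility comes from defining safety as non-significance with 25 per arm, which longer follow-up would not cure. All of this stands, and it rules out any claim that the verdict would change.

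**Pilot setting.** Ending follow-up at transfer is understandable in a single-system pilot focused on recruitment and adherence. But this plan attaches its own verdict rule to safety.

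**Conclusion.** The point holds as a gap in design and analysis. As written, Design stops observation at transfer within the primary safety window, and no rule says how the patient is then analysed by intention to treat. A first qualifying event between transfer and month 3 may go unobserved. That is firm for additional sessions at an outside unit and conditional on the meaning of study end for hospitalizations and deaths. Unobserved intervention-arm events push toward the favourable verdict.

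The size cannot be established from the documents. If few patients transfer, and for reasons unrelated to outcome, the effect is small. Near the significance boundary a single lost event can decide the result. The p-values and power figures rest on assumed counts, risks and losses, and they do not show that the trial's verdict would be wrong. The change is worth making because it is inexpensive and the missing events cannot be recovered reliably later.

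**What to change.** 1. Reconcile Design and Data collection, and define study end. State that transfer of care ends study assessments and urine collections. Unless consent is withdrawn, it should not end collection of the events listed under Primary safety outcomes to month 3, or of vital status to month 12.
2. Name the sources: contact with the patient and records from the receiving unit, explicitly including additional dialysis sessions.
3. In the Analytical Plan, state how patients with incomplete month-3 safety data enter the main comparison. Report their number by arm, and add a sensitivity analysis that counts them as events.

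The cost is a few protocol sentences, a line of consent or authorization, and a small number of record requests by existing staff. The consent pages are not in the copy reviewed, so authorization may already exist. Telephone contact alone will not reliably establish cause or laboratory values, and some outside events may lack the values needed to classify them; these should be reported as unclassified. No treatment changes.

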Assessment of volume status will use the following surrogate markers of volume overload: IDWG >2.5kg, relative IDWG >5.7% of the TW, and UFR >10ml/kg/hr. Events of volume overload will be compared between study groups as proportion of markers of volume overload of the total measurements of IDWG and UFR achieved with each HD treatment during the first 3 months, stratified in two periods (week 1 to 6 and week 7 to 12).

- Hospitalization rate

Time point: end of follow-up

Time to first hospitalization, cause of hospitalization and length of stay will be recorded and compared between treatment arms.

- Quality of life, Depression and Anxiety

Time points: weeks 6 & 12

The Dialysis Symptom Index questionnaire will be used to assess participant health-related quality of life. This is a short form that measures the burden of kidney disease, symptoms/problems of kidney disease, and effects of kidney disease scales. The score range is 0-100 with higher scores denoting better outcomes. Depression will be assessed using the PHQ-9 instrument. Anxiety will be assessed using the GAD-7 instrument.

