### ***Exploratory outcome***

- Patient survival

Timeframe: end of follow-up

The tertiary outcome will consist of exploratory analyses to compare the mortality rate between the two schedules of HD.

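### Time to first hospitalization is planned by Kaplan–Meier with no rule for death before admission, so the proportion admitted would by default be slightly overstated; a minor point on one secondary outcome.

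*Combined protocol and SAP*

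**What the plan says.** - **Follow-up (Design).** The planned period is one year from randomization. It stops early for some patients: "or until transplant, death, withdrawal of consent, or transfer of care outside Wake Forest healthcare system, whichever occurs sooner".
- **Outcome (Secondary outcomes, Hospitalization rate).** The time point is the end of follow-up. "Time to first hospitalization, cause of hospitalization and length of stay will be recorded and compared between treatment arms".
- **Method (Analytical Plan).** "Kaplan–Meier methods will be used for time-to-first hospitalization analyses". The plan names no other method for this outcome. It gives no censoring rule, no cumulative incidence estimate, and no end point that combines admission with death.
- **Where deaths are counted.** Data collection: "All hospitalizations and deaths (along with the cause) will be recorded from the time of enrollment to study end". Exploratory outcome: "The tertiary outcome will consist of exploratory analyses to compare the mortality rate between the two schedules of HD". The 3-month primary safety definition has as its last item "5) death associated with study intervention". The Analytical Plan also lists a higher death rate in the intervention arm among the signals to be reported for a decision on the study's continuation.

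**The concern.** Kaplan–Meier estimates the admission risk that would apply if censored patients went on to face the same risk as those still followed. That is a reasonable idealization for a patient who moves away. It is not one for a patient who has died, because that patient can never be admitted. Death before a first admission is a competing event. If it is censored, one minus the Kaplan–Meier estimate no longer equals the proportion of the arm that was admitted.

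Two things are at stake. The reported 12-month admission probability would be too high, by an amount that depends on each arm's death rate. And if one arm had more deaths outside hospital, its first-hospitalization curve would not show it. This matters somewhat in a study that the protocol itself describes as high risk and in which excess hospitalization is a named safety signal.

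**Working it through.** **Inputs from the documents.** Follow-up is 12 months, there are 25 patients per arm, and Kaplan–Meier is the only method named. The sample size was chosen for feasibility, and the documents give no admission, death or transplant rate. There is therefore no stated figure to reproduce beyond 2 × 25 = 50.

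**Assumptions.** Hazards are constant and independent over one year: *h* for first admission and *d* for death. Every rate below is assumed.

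**Formulas at one year.**
- One minus Kaplan–Meier, with deaths censored: 1 − exp(−h)
- Cumulative incidence of admission (what Aalen–Johansen estimates): h/(h+d) × [1 − exp(−(h+d))]
- Cumulative incidence of death before admission: d/(h+d) × [1 − exp(−(h+d))]

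**Worked case.** Let one minus Kaplan–Meier be 50%, so h = −ln 0.50 = 0.693. Let the 12-month death risk be 20%, so d = −ln 0.80 = 0.223. Then exp(−(h+d)) = 0.50 × 0.80 = 0.40. The cumulative incidence of admission is 0.693/0.916 × 0.60 = 45.4%. The excess is 50.0 − 45.4 = 4.6 points, or 25 × 0.046 = about 1.2 patients in an arm.

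**Range, with one minus Kaplan–Meier fixed at 50%.**

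| 12-month death risk | Truly admitted | Excess (points) | Patients per arm of 25 |
|---|---|---|---|
| 0% | 50.0% | 0 | 0 |
| 5% | 48.9% | 1.1 | 0.3 |
| 10% | 47.7% | 2.3 | 0.6 |
| 20% | 45.4% | 4.6 | 1.2 |
| 30% | 42.9% | 7.1 | 1.8 |

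Over death risks of 5% to 30%, the excess is 0.7 to 4.5 points if Kaplan–Meier gives 30%, and 1.4 to 9.1 points if it gives 70%. A simulation with 25 per arm at the 50% setting, for death risks of 5%, 10% and 20%, agreed with the formulas.

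**Sampling error for scale.** The 95% half-width for one arm at 50% is about 1.96 × √(0.5 × 0.5/25) = 0.196, or about 20 points.

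**Between arms.** Give both arms the same admission hazard (50%) but death risks of 5% and 20%.
- One minus Kaplan–Meier: 50.0% in both, so the extra deaths are invisible.
- Cumulative incidence of admission: 48.9% v 45.4%.
- Death before admission: 3.6% v 14.6%.
- Admission or death (the sum of the last two): 52.5% v 60.0%.

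The admission curve taken alone therefore favors the arm with more deaths. A more extreme case shows it more sharply. With h = 1.0 per year in both arms and d = 0.40 v 0.05, cumulative incidence of admission is 53.8% v 61.9%. Any replacement has to show deaths next to admissions.

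**The case against.** There is a strong case that little is wrong here.

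**Deaths are counted.** A reader might infer that a patient who dies before admission never counts against an arm. The documents do not support that. All deaths are recorded, mortality is compared as an exploratory outcome, excess deaths are a monitoring signal, and intervention-associated death is in the 3-month safety definition. The gap is confined to the first-hospitalization analysis.

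**The between-arm test is not broken.** A reader might also infer that the comparison of arms is invalid. A log-rank test that censors deaths compares cause-specific admission hazards, which is a legitimate target. In simulation with equal admission hazards and death hazards of 0.4 v 0.05 per year, it rejected in about 5% to 6% of trials, near the nominal level. The plan names no test, so it should name this one and say what it compares.

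**A composite is not clearly better.** In that same extreme scenario, admission-or-death rejected in about 13% to 15% of trials, while a direct log-rank comparison of mortality rejected in about 77%. At 0.2 v 0.05 per year the composite reached only 6% to 7%, against about 5% for admission alone. Replacing the end point would mix two events for almost no gain.

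**Transplant is not death.** A transplanted patient can still be hospitalized. Transplant competes only if the target is admission while on dialysis. Otherwise it is censoring, possibly informative. The plan does not say which is meant.

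**Censoring at death is inferred.** The plan does not state it, nor that one minus Kaplan–Meier will be reported as the proportion admitted.

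The first four objections stand and limit the point. The last stands only in part: censoring at death is the ordinary reading of follow-up that ends at death combined with an unqualified Kaplan–Meier analysis. If something else is intended, the plan still needs to say so.

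**Conclusion.** The point holds in a narrow form, and its severity is minor. If deaths before admission are censored, one minus Kaplan–Meier overstates the 12-month proportion admitted whenever such a death occurs, and those deaths do not register in this one analysis. The direction is certain under that reading. The size rests wholly on assumed rates with constant, independent hazards: about 1 to 5 points at 50% admission and 5% to 20% death. That is well below the sampling error of about 20 points, and it is zero if nobody dies before admission.

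Nothing in the four feasibility criteria, the progression decision, the sample size or the 3-month safety outcome depends on it. It is still worth correcting because the better estimate is nearly free.

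**What to change.** Amend the Hospitalization rate entry under Secondary outcomes and the Analytical Plan as follows.

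1. Report first hospitalization by arm as Aalen–Johansen cumulative incidence, with death as a competing event.
2. Beside it, show the cumulative incidence and count of death before admission by arm. Without this, an arm with more deaths can look better on admissions.
3. State the target for transplant. If it is admission while on dialysis, treat transplant as a competing event; otherwise treat it as censoring. Either way, give its count by arm.
4. Compare arms by a log-rank test, labelled as a comparison of cause-specific admission hazards.
5. Add time to first hospitalization or all-cause death as a sensitivity analysis only. If transplant is treated as competing, handle it the same way here, because Kaplan–Meier on the composite would otherwise have the same defect.

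**Cost.** Analysis-plan wording and one extra curve. Hospitalizations and deaths are already recorded. Transplant is not in that recording list, but its date must be known because it ends follow-up. The one visible consequence is a slightly lower reported admission probability.
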